2.4 HANDLING OF MISSING DATA

As a general rule, missing data values are not imputed unless otherwise specified and, in presentation of categorical variables, unknown and missing data may be presented as a separate category and the denominator will include unknown or missing values as appropriate.

2.5 PROTOCOL DEVIATIONS

2.5.1 ESA and Parenteral Iron Dose-Adjustments

Selected types of ESA dose adjustments will be summarized by treatment using descriptive statistics, including:

- Change in the total weekly dose of EPOGEN during Weeks 1-4 compared with the Week - 2 or Week -1 dose

- Change in the total dose of ARANESP or MIRCERA during Weeks 1-4 compared with the mean weekly dose during screening (based on the last 2 doses prior to randomization) multiplied by 4.
- Start of parenteral or dialysate iron during Weeks 1- 4 in a patient not receiving parenteral or dialysate iron during the 3 weeks prior to randomization
- Discontinuation of parenteral iron during Weeks 1- 4 in a patient receiving parenteral or dialysate iron during the 3 weeks prior to randomization
- Change in the total dose of parenteral elemental iron during Weeks 1-4 compared with the mean weekly dose during Weeks -3, -2, and -1 multiplied by 4.
- More than one ESA dose increase in any 4-week period after Week 4.

The ESA and parenteral iron dosing guidelines in the protocol are as follows:

Weeks 1 - 4

- ESA doses are not to be adjusted or held during Weeks 1 through 4 unless one or more confirmed hemoglobin values (i.e., at least 2 consecutive measurements) or the patient's clinical status necessitates such due to a clear and present safety risk.
- Parenteral iron doses are not be adjusted or held during Weeks 1 through 4.
- Patients not receiving parenteral iron products during Screening must not be started on these during Weeks 1 through 4.
- The Medical Monitor must be contacted prior to any contemplated ESA or parenteral iron dose changes.

Weeks 5 – 24

- Changes to ESA dosing must be based on hemoglobin values that have been confirmed (i.e., at least 2 consecutive measurements).
- Do not increase the dose more frequently than once every 4 weeks. The recommended dose increase at any given time is 25%.
- Decreases in dose may occur more frequently than once every 4 weeks. The recommended minimum duration between dose reductions is 3 weeks.
- If the hemoglobin rises rapidly (e.g., more than 1 g/dL in any 2-week period), reduce the dose by 25%. A greater reduction may be made, if rise in hemoglobin is unacceptably rapid.
- The Medical Monitor must be contacted prior to any contemplated ESA dose changes that depart from the above protocol requirements and recommendations unless clinical urgency precludes this. If the Medical Monitor is not contacted in advance, please send a notification within 24 hours that an off-protocol ESA dose change was made.
- Patients not receiving parenteral iron products must not be started on these during Weeks 5 through 24.
- Parenteral iron doses are not to be adjusted or held during Weeks 5 through 24, unless approved

by the Medical Monitor.

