No change in the total weekly dose during Week -1 compared with Week -2.
 - For ESAs dosed less often than weekly:***
Any dose given during Full Screening Week -2 and Week -1 is unchanged from the immediately preceding dose.
 - Note: If a dose was given on both Week -2 and Week -1, then both doses are the same. (These 2 doses may be different than earlier doses).

10. Has been receiving intravenous (IV) or dialysate iron regularly and continuously (e.g., with each dialysis or each week) during the 3 weeks prior to randomization OR has received no IV or dialysate iron during this time frame and use of IV or dialysate iron is not anticipated through Study Week 24.
 - If parenteral iron has been administered during the 3 weeks prior to randomization, the regimen has been stable (same elemental iron dose, same frequency, and same iron product) with no more than 2 missed or held doses if dosed with each dialysis and no missed or held doses (if dosed weekly or less frequently) during this time frame.

11. If receiving oral ferric citrate, the patient has been prescribed it for at least 2 weeks prior to Full Screening and the dose is not anticipated to be changed through Study Week 24.

12. At least 2 ferritin values during Screening > 300 ng/mL.

13. At least 2 TSAT values during Screening between 15% and 50% (inclusive).

14. ESA resistance index (confirmed by the Sponsor) during the 2 weeks prior to randomization:

For patient receiving epoetin alfa:

$$\frac{\text{Total weekly dose of epoetin alfa (units)}}{(\text{hemoglobin [g/dL]} * \text{target dry body weight [kg]})} > 8 \text{ units/kg per g/dL}$$

For patients receiving darbepoetin alfa:

$$\frac{\text{Total weekly dose of darbepoetin alfa (mcg) * 300}}{(\text{hemoglobin [g/dL]} * \text{target [kg]})} > 8 \text{ units/kg per g/dL}$$

For patients receiving methoxy polyethylene glycol-epoetin beta:

$$\frac{\text{Weekly dose of methoxy polyethylene glycol-epoetin beta (mcg) * 300}}{(\text{hemoglobin [g/dL]} * \text{target dry body weight [kg]})} > 8 \text{ units/kg per g/dL}$$

If the ESA is dosed less often than once a week, divide the dose by the dosing interval to determine the weekly dose. For example, Weekly dose = dose given every two weeks ÷ 2.

The first day of each week used for calculations is defined as the first dialysis day of the Week (i.e., Monday or Tuesday).

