Appendix C ESA and Parenteral Iron Dose-Adjustments

Weeks 1 - 4

- ESA doses are not to be adjusted or held during Weeks 1 through 4 unless one or more confirmed hemoglobin values (i.e., at least 2 consecutive measurements) or the patient's clinical status necessitates such due to a clear and present safety risk
- Parenteral iron doses are not to be adjusted or held during Weeks 1 through 4
- Patients not receiving parenteral iron products during Screening must not be started on these during Weeks 1 through 4
- The Medical Monitor must be contacted prior to any contemplated ESA or parenteral iron dose changes

Weeks 5 – 24

- Changes to ESA dosing must be based on hemoglobin values that have been confirmed (i.e., at least 2 consecutive measurements)
- Do not increase the dose more frequently than once every 4 weeks. The recommended dose increase at any given time is 25%
- Decreases in dose may occur more frequently than once every 4 weeks. The recommended minimum duration between dose reductions is 3 weeks
- If the hemoglobin rises rapidly (e.g., more than 1 g/dL in any 2-week period), reduce the dose by 25%. A greater reduction may be made, if rise in hemoglobin is unacceptably rapid
- The Medical Monitor must be contacted prior to any contemplated ESA dose changes that depart from the above protocol requirements and recommendations unless clinical urgency precludes this. If the Medical Monitor is not contacted in advance, please send a notification within 24 hours that an off-protocol ESA dose change was made
- Patients not receiving parenteral iron products must not be started on these during Weeks 5 through 24
- Parenteral iron doses are not to be adjusted or held during Weeks 5 through 24, unless approved by the Medical Monitor

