- The intervals that will be described are Weeks 1-4, 5-8, 9-12, etc through Week 24. In addition, Weeks 8-12 (the endpoint) and Weeks 1-12 will be described.

Parenteral iron doses are generally expected to be administered weekly, every other week, or with each dialysis. Parenteral iron doses will be summarized based on elemental iron contained within the iron product administered. All parenteral iron products will be combined for the analyses. If dose units are reported in mL, these will be converted to mg of elemental iron as follows:

IRON PRODUCT	ELEMENTAL IRON
Ferric gluconate (e.g. Ferrlecit)	12.5 mg per mL
Ferumoxytol (e.g. Feraheme)	30 mg per mL
Ferric carboxymaltose (e.g. Ferinject)	50 mg per mL
Ferric pyrophosphate citrate (e.g. Triferic)	5.44 mg per mL
Iron sucrose (e.g. Venofer)	20 mg per mL

Post-randomization parenteral iron doses will be summarized in a similar way to ESA. No analyses will be performed using individual parenteral products, however.

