7.5 SENSITIVITY ANALYSES

Key anemia-related PD endpoints will be summarized separately for patients with and without off protocol ESA dosing. Protocol ESA dosing is defined in [Section 2.5.1](#). The secondary and other PD endpoints based on measurements of TSAT, ferritin, CHr, hypochromic RBC, reticulocyte count, and hemoglobin will undergo the sensitivity analyses. These analyses will exclude patients who have off-protocol dosing of ESAs or iron during Weeks 1 – 4 as defined in [Section 2.5.1](#).

Because hospitalizations are associated with multifactorial reduction in hemoglobin and missed ESA doses, a sensitivity analysis will be performed of the above two analyses in which analyses of ESA doses, ERI, and hemoglobin after the start date of the first SAE will be excluded.

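### The iron-change test in SAP 2.5.1 uses a three-week baseline that unchanged every-other-week iron can never match, and the SAP 7.5 iron exclusion stops at Week 4 although it serves endpoints at Weeks 10-12

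*SAP*

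**What the plan says.** SAP 2.5.1 opens its list of dosing deviations with "Selected types of ESA dose adjustments will be summarized by treatment using descriptive statistics, including". Three of the items concern iron, and all three are limited to Weeks 1-4: starting it, discontinuing it, and a change in total dose. The last compares "parenteral elemental iron during Weeks 1-4 compared with the mean weekly dose during Weeks -3, -2, and -1 multiplied by 4". No tolerance is given. The only item that looks beyond Week 4 concerns ESA increases. The section then restates the protocol's ESA and iron dosing guidelines.

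On frequency, SAP 6 says: "Parenteral iron doses are generally expected to be administered weekly, every other week, or with each dialysis". Inclusion criterion 10 (Protocol 4.1) admits patients on each-dialysis iron with "no more than 2 missed or held doses if dosed with each dialysis" in the three weeks before randomization, and otherwise requires "no missed or held doses (if dosed weekly or less frequently) during this time frame".

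SAP 7.5 applies its sensitivity analyses to the secondary and other endpoints built on TSAT, ferritin, CHr, hypochromic red cells, reticulocytes and hemoglobin. It states: "These analyses will exclude patients who have off-protocol dosing of ESAs or iron during Weeks 1 – 4", and refers to 2.5.1 for the definition. SAP 7.2 places TSAT, CHr and hemoglobin endpoints at Weeks 10-12 as well as at Week 4.

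Protocol Appendix C bars new parenteral iron in Weeks 5-24 and adds: "Parenteral iron doses are not to be adjusted or held during Weeks 5 through 24, unless approved by the Medical Monitor".

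**The concern.** Parenteral iron bears directly on TSAT, ferritin, CHr and hemoglobin, so the plan needs a sound way to tell a stable background regimen from a changed one. Two features of the present rule work against this.

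- **Baseline length.** A three-week baseline scaled to four weeks does not contain a whole number of two-week dosing intervals. With no tolerance, a patient whose iron never changed can be recorded as changed.
- **Window.** The iron exclusion looks only at Weeks 1-4, while some of the endpoints it is meant to protect are measured at Weeks 10-12. A patient newly started on iron in Week 8, contrary to Appendix C, meets no iron criterion in 2.5.1 and is not excluded under 7.5.

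At stake are the accuracy of the reported off-protocol iron dosing and the usefulness of the sensitivity analysis for the anemia-related endpoints.

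**Working it through.** The documents give no figure for this rule, so there is none to reproduce. The check applies the SAP formula to unchanged regimens.

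**Inputs**
- Reference R = (iron given in Weeks -3 to -1) / 3 × 4, from SAP 2.5.1.
- Observed O = iron given in Weeks 1-4, from SAP 2.5.1.
- Apparent change = (O - R) / R.
- Regimens: weekly, every other week and each dialysis, from SAP 6.
- Missed screening doses: up to 2 for each-dialysis iron, from criterion 10.
- Assumption: each-dialysis iron means 3 doses per week, in line with the three weekly sessions in Protocol 3.6.

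**Step 1: unchanged regimens, in units of one dose**

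| Regimen | Doses in 3 weeks | R | O | Apparent change |
|---|---|---|---|---|
| Weekly | 3 | 3/3 × 4 = 4 | 4 | 0% |
| Every other week | 1 | 1/3 × 4 = 1.33 | 2 | +50% |
| Every other week | 2 | 2/3 × 4 = 2.67 | 2 | -25% |
| Each dialysis, none missed | 9 | 9/3 × 4 = 12 | 12 | 0% |
| Each dialysis, 1 missed in screening | 8 | 8/3 × 4 = 10.67 | 12 | +12.5% |
| Each dialysis, 2 missed in screening | 7 | 7/3 × 4 = 9.33 | 12 | +28.6% |

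For every-other-week iron there are 14 possible day offsets between the schedule and Day 1. Seven give +50%, seven give -25% and none gives 0%. The reason is general: with k equal doses at baseline, R = 4k/3 doses, which is a whole number only when k is a multiple of 3. With k = 1 or 2, no count of full doses in Weeks 1-4 can match it.

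**Step 2: does the test separate compliance from deviation?** Suppose one every-other-week dose is held in Weeks 1-4, so O = 1.
- With 1 baseline dose: (1 - 1.33)/1.33 = -25%.
- With 2 baseline doses: (1 - 2.67)/2.67 = -62.5%.

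The first result equals that of a fully compliant patient with 2 baseline doses.

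**Step 3: would a tolerance help?** The SAP states none, so these are assumptions about every-other-week iron, with a change counted only if it exceeds the tolerance.
- Below 25%: all 14 offsets are still flagged.
- From 25% to just under 50%: 7 of 14 are flagged.
- 50% or more: none is flagged, but the held dose that scores -25% in Step 2 is missed.

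**Step 4: baselines that fit the interval.** For unchanged every-other-week iron:
- 2-week baseline: 1/2 × 4 = 2 against 2.
- 4-week baseline: 2/4 × 4 = 2 against 2.
- Last two doses, as SAP 2.5.1 already does for ARANESP and MIRCERA: 2 doses over 4 weeks, × 4 = 2 against 2.

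The apparent change is 0% each time, at every offset for the 2- and 4-week baselines.

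**Step 5: windows side by side**
- Iron restrictions: Weeks 1-24 (Appendix C, restated in SAP 2.5.1).
- Iron criteria in SAP 2.5.1: Weeks 1-4.
- Iron exclusion in SAP 7.5: Weeks 1-4.
- Endpoints covered by 7.5: Week 4 and Weeks 10-12, among others.

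The exclusion fits the Week 4 endpoints. For the Weeks 10-12 endpoints, Weeks 5-12 are uncovered for iron.

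**The case against.** The strongest objection is that the 2.5.1 items are introduced as descriptive output, not as an exclusion rule. The same section restates the dosing guidelines, and the reference in 7.5 fits those equally well. On that reading a patient on unchanged every-other-week iron is compliant and stays in. This stands as far as it goes: a reader might infer that compliant patients are certain to be dropped, and the documents do not support that. They do not rule it out either. The listed items are the only computable test, and SAP 2.5.2 keeps ESA and iron deviations out of its query, review and tracker route. On either reading the 2.5.1 summary still reports false changes, and the Week 4 limit remains because it is written into 7.5 itself.

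Other tempting readings also go too far:

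- **That 7.5 is the only safeguard.** SAP 6 summarizes iron doses in a similar way to ESA doses, by interval. SAP 7.3 examines iron requirements at Weeks 8-12 and through Week 24. One hemoglobin endpoint in SAP 7.2 drops values after an ESA change above 25%. The pharmacodynamic population in SAP 2.2 can exclude important deviations before unblinding. That last route could catch a late iron start, but it depends on judgment and names no iron criterion.
- **That the late gap covers ESA as well.** The other split in 7.5, by off-protocol ESA dosing, carries no Week 4 limit, and 2.5.1 has an ESA item after Week 4.
- **That every late iron change is a violation.** Adjusting or holding iron in Weeks 5-24 is allowed with Medical Monitor approval. Only new starts and unapproved changes are barred.
- **That the long-acting ESA item has the same fault.** This needs an interval such as three weeks, which the documents do not mention.

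It is also fair to say that Weeks 1-4 is the period of strictest dose stability, and that excluding on later dosing conditions on events after randomization that treatment may influence. This argues for making a later-window analysis supplementary, not for leaving it out.

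**Conclusion.** The point holds. As written, the iron comparison in SAP 2.5.1 reports a false change of +50% or -25% for every patient on unchanged every-other-week iron, a frequency the SAP itself expects. It also reports +12.5% or +28.6% for each-dialysis patients who qualified with one or two permitted missed doses and then returned to full dosing. These results assume equal doses, that any nonzero difference counts as a change, and, for the each-dialysis figures, three doses per week.

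Whether compliant patients also leave the sensitivity analysis depends on which part of 2.5.1 governs 7.5, and the SAP does not say. The Week 4 limit on the iron exclusion is a separate gap that matters only for the later endpoints.

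The practical size is unknown, because the documents do not give the number of patients on every-other-week iron or with missed screening doses. Only deviation summaries and sensitivity analyses of secondary and other pharmacodynamic endpoints are affected. A reader should not extend the point to the maximum tolerated dose assessment or to hsCRP and SAA, which are not among the measurements SAP 7.5 lists.

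**What to change.** 1. **SAP 2.5.1:** base the iron comparison on whole dosing intervals. For iron given less often than weekly, use the last-two-doses approach already specified for ARANESP and MIRCERA; for each-dialysis iron, compare with the prescribed regimen. Alternatively, define a change as a change in product, dose per administration or interval.
2. **SAP 7.5:** state that this definition governs the exclusion, so that the reference to 2.5.1 has one meaning.
3. **Late endpoints:** keep the Weeks 1-4 exclusion and add a supplementary sensitivity analysis of the Weeks 10-12 endpoints that also flags iron starts and unapproved iron changes in Weeks 5-12.

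No dosing rule in the protocol changes. The cost is SAP wording and a little programming on dosing records. Approval of late iron changes must be traceable, and the documents do not say where it is recorded. The late-endpoint set may be smaller, and the added analysis conditions on dosing after randomization, as the existing Weeks 1-4 exclusion already does.

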2.5.2 Other Deviations

Protocol deviations other than those related to ESA and iron dosing will be identified by a combination of programmatic query of the database, manual data review, and the clinical operations protocol deviation tracker.

2.6 ANALYSIS SOFTWARE

The pharmacokinetic (PK) evaluation and PK/PD modeling will be performed by an independent pharmacometrician (██████████). All other summaries and statistical analyses will be generated using SAS® version 9.2 or later. See Data Analysis Plan for Pharmacokinetic and Pharmacokinetic-Pharmacodynamic Modeling.

3. STUDY SUBJECTS

3.1 DISPOSITION OF SUBJECTS

The number of subjects screened and the number (percent) of subjects who failed screening and the reasons for screen failure will be summarized, as available, based on data reported on the Screening Failure CRF. The distribution of the number of randomized subjects enrolled will be summarized for each randomized treatment group in each dosing regimen (combining all placebo patients as one control group) and overall based on the ITT analysis population.

The number (percent) of randomized and treated subjects who completed treatment will be summarized by treatment group based on the ITT analysis population. The subjects discontinued from study treatment will be summarized according to the reasons for discontinuation, based on data reported on the End-of-Study CRF.

The number (percent) of randomized subjects who completed the study and who discontinued from the study will be summarized according to the reasons for discontinuation, based on data reported on the End-of-Study CRF.

4. DEMOGRAPHICS AND BASELINE CHARACTERISTICS

4.1 DEMOGRAPHICS AND BASELINE CHARACTERISTICS

Demographic and baseline characteristics will be summarized by treatment group using descriptive statistics for the ITT, pharmacodynamic, and safety analysis populations. Continuous demographic and baseline variables include age, pre-dialysis weight at week -1, post-dialysis weight at week -1, height, body mass index (BMI) based on post-dialysis weight at week -1; categorical variables include sex, race, and ethnicity.

4.2 DIALYSIS SIGN AND SYMPTOMS

The number (percent) of subjects with each specific dialysis sign and symptom as recorded on the CRF will be summarized by treatment group and overall for safety analysis population.

4.3 MEDICAL HISTORY

- Kidney Disease History

Kidney disease history will be summarized separately from other medical histories. The duration of end stage renal disease (ESRD), Single pool Kt/V (spKt/V) within 8 weeks prior to the full Screening Period, number (percent) of subjects with kidney transplant, status of the transplanted kidney, primary cause of chronic kidney disease and dialysis access used during Week -2 will be summarized by treatment group and overall for safety analysis population.

- Selected Medical History

The number (percent) of subjects reporting selected medical history, including cardiovascular history, infection history and other history as recorded on the CRF, will be summarized by treatment group and overall for safety analysis population.

- Other Medical History

The other medical history verbatim descriptions (investigator terms from the CRF) will be classified into medical terminology using the Medical Dictionary for Regulatory Activities (MedDRA). Events will be coded to primary System Organ Class (SOC) and preferred term (PT) using MedDRA Version 19.0. The prevalence of medical history events will be reported as the number (percent) of subjects by treatment group, SOC and PT for safety analysis population.

5. STUDY DRUG AND EXPOSURE

5.1 TREATMENT COMPLIANCE

Since the study drug will be administered as an intravenous infusion, the treatment compliance will not be provided. Information regarding study drug administration will be provided in data listings.

5.2 EXTENT OF EXPOSURE

Study drug will be administered by infusion once every other week for 11 weeks (6 doses) for the planned treatment regimens in the protocol. Exposure will be summarized using the cumulative frequency and percentage of subjects receiving ≥ 1 dose, ≥ 2 doses, ... ≥ 5 doses, and 6 doses by treatment group. Descriptive statistics (number of subjects, mean, standard deviation, minimum, median, quartiles range, and maximum) for exposure will be summarized. In addition, the exposure (in days), defined as the date of the last dose of study drug – date of the first dose of study drug + 1 will be summarized. Exposure with respect to COR-001-01 blood levels will be described in the Pharmacokinetics and Pharmacokinetic-Pharmacodynamic Modeling Data Analysis Plan.

5.3 PRIOR AND CONCOMITANT THERAPY

Erythropoiesis-stimulating agents and parenteral iron doses will be separately summarized (see [Section 6](#)).

All investigator terms for medications recorded on the CRF will be coded using the World Health Organization (WHO) Drug Dictionary. The number (percent) of subjects who took prior and concomitant medications will be summarized on the safety analysis population by treatment group, dose and Anatomical Therapeutic Chemical (ATC) Classification and WHO Drug preferred term.

